11.2 Statistical Methods

Data will be analysed by the Study Statistician. Results will be presented as 2x2 tables for the whole study population. The sensitivity and specificity of POC testing are the main constituents of the primary outcome measure of the study. An assessment of the diagnostic accuracy of the POC device will be based on these measures and on positive and negative predictive values calculated from comparison with conventional culture as the reference standard. The data supporting an assessment of diagnostic accuracy will be reported according to STARD³⁸ criteria, including explanations of losses of participants. The possible effects of heterogeneity in the study population will be examined and separate sub-analyses for the different types of patients recruited will be performed. These will provide assessments of the validity of POC testing by this method and device in the context of prior antimicrobial exposure, varying underlying diagnoses and by patient condition.

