5. OUTCOME MEASURES

5.1 Primary Outcome Measure

The primary outcome measure is diagnostic accuracy of the multiplex PCR test, expressed as sensitivity, specificity, and positive and negative predictive values, with uncertainty expressed using 95% confidence limits.

In the primary analysis, these will be calculated by using the paired blood culture as the reference standard (i.e. the blood culture that had been taken contemporaneously). True positivity will be defined as the PCR test detecting the same genus of organism as identified in the paired blood culture.

Acknowledging that there is no perfect reference standard for sepsis, a secondary analysis will be undertaken, using a less stringent reference standard to resolve discrepant results in a 'fair umpire' test³⁷. This will be applied when the PCR test is positive and the paired blood culture is negative. In this analysis, true positivity will be defined as either:

- (i) culture of the same genus of organism in blood or other sterile site culture within 7 days of the test sample being taken; or
- (ii) culture of the same genus of organism from a non-sterile anatomic site within 3 days of the test sample being taken which is judged, by the patient's clinical team, to represent a focus of infection.

Furthermore we will undertake analysis of the primary outcome measure when multiplex PCR testing is conducted at the point of care, vs. centrally, using both the paired blood culture and the fair umpire test. The primary outcome (diagnostic accuracy) will be re-analysed including only those samples tested at the point of care and compared to the same metrics obtained when only those samples tested centrally are included.

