9.2.2.1 Sample for Multiplex PCR Testing

Approximately the first half of the study samples will be initially stored at site and transferred in batches to a central laboratory in Queen's University Belfast, for testing using the Multiplex PCR device, in accordance with the Sample Processing Guideline. Subsequent samples will be analysed using the Multiplex PCR device at the POC by ICU clinical and/or research and/or technical staff at participating sites who have received training in the use of the Multiplex PCR testing device and transferred in batches to a central laboratory in Queen's University Belfast for testing using the Multiplex PCR device.

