11. STATISTICAL CONSIDERATIONS

11.1 Sample Size

The sample size is based on:

- (i) an assumed 10% event rate for true positive results among specimens collected – this is based on pilot data collected in a single centre.
- (ii) an estimated overall test sensitivity of 90%, and specificity of 95%.
- (iii) the need to ensure that the overall test sensitivity is estimated with a high degree of precision. We have set this precision as +/-3%, at the 95% confidence level.
- (iv) the ability to assess performance of the test for detecting pathogens for which true positive results are expected as infrequently as 1 in 500 tests. We have set the precision for this as +/-20%, at the 95% confidence level
- (v) Given a 10% event rate for true positive results, a sample size that achieves the proposed degrees of precision for the sensitivity estimate will enable the specificity of the test to be measured with even greater precision.

With an assumed sensitivity of 90% with a 10% true positivity rate, in order to estimate the overall sensitivity of the test with a precision of +/-3% at the 95% confidence level, 3851 samples are required. For uncommon pathogens, with an assumed sensitivity of 90% with a 0.2% true positivity rate, in order to estimate the overall sensitivity of the test with a precision of +/-20% at the 95% confidence level, 4501 samples are required. Therefore, 4501 samples will be tested to assess the diagnostic accuracy of the test using these parameters.

The sample has not been inflated for dropouts or missing data because: (i) research sampling is not necessary after the day of enrolment; (ii) the follow-up period is very short; and (iii) the nature of ICU care presents minimal risk of attrition for follow-up.

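### Section 5.1 compares crude predictive values between point-of-care and central samples; unless limited to samples tested both ways, PPV can differ with an unchanged device

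*Protocol*

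**What the plan says.** Protocol section 5.1 defines the primary outcome as diagnostic accuracy, "expressed as sensitivity, specificity, and positive and negative predictive values, with uncertainty expressed using 95% confidence limits". It then plans to recalculate this outcome using only samples tested at the POC, and the result is to be "compared to the same metrics obtained when only those samples tested centrally are included". The two predictive values are among those metrics. The section does not say whether the central set is the early samples, every sample with a central result, or only samples with both results.

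Section 9.2.2.1 decides which samples have which result. "Approximately the first half of the study samples will be initially stored at site and transferred in batches to a central laboratory", so these have a central PCR result only. Later samples are run at the POC and then also sent in batches for central testing, so they have both.

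Section 11.2 ranks the metrics: "The sensitivity and specificity of POC testing are the main constituents of the primary outcome measure of the study". It adds the predictive values to the overall assessment ("An assessment of the diagnostic accuracy of the POC device will be based on these measures and on positive and negative predictive values"). It also plans sub-analyses by type of patient: "These will provide assessments of the validity of POC testing by this method and device in the context of prior antimicrobial exposure", and by diagnosis and condition. It names no metric for these. Neither section mentions standardising predictive values or reading them alongside culture positivity.

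**The concern.** PPV and NPV depend on the share of samples that are positive on the reference standard, as well as on sensitivity and specificity. If the POC set and the central set differ in culture positivity, their crude PPVs differ even when the device performs identically in both.

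The allocation makes such a difference possible. Central-only testing is assigned by calendar order, and section 11.1 takes its 10% positivity from a single-centre pilot. The POC-versus-central comparison is meant to show whether moving the device to the bedside changes its accuracy. A PPV gap caused by positivity could be read as a gain or a loss from bedside testing.

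The distortion can also hide a real loss. At sensitivity 80%, specificity 95% and 12% positivity, PPV is 0.096/(0.096 + 0.044) = 68.6%. That is slightly above the 66.7% obtained at sensitivity 90% and 10% positivity.

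**Working it through.** **Inputs from the protocol (section 11.1).** Sensitivity (Se) 90%, specificity (Sp) 95%, positivity p = 10% ("an assumed 10% event rate for true positive results among specimens collected"), total 4501 samples. Half of 4501 is about 2250. Positivity by phase or by set is not given. I assume 5% to 15% around the stated 10%.

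**Reproducing the plan's own figures.** Positives needed = 1.96² × Se × (1 − Se) / d², rounded up, then divided by positivity.
- Overall, d = 3%: 384.1, rounded up to 385; 385/0.10 = 3850 (stated 3851).
- Uncommon pathogens, d = 20%: 8.64, rounded up to 9; 9/0.002 = 4500 (stated 4501).

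Both agree to within one sample. The calculation treats the 10% as the reference-positive fraction, and I use it in that sense.

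**Predictive values with the device held constant.**

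PPV = Se·p / [Se·p + (1 − Sp)(1 − p)]

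NPV = Sp(1 − p) / [Sp(1 − p) + (1 − Se)p]

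| Culture positivity | PPV | NPV | Expected PCR positives in 2250 |
|---|---|---|---|
| 5% | 48.6% | 99.4% | 208 |
| 8% | 61.0% | 99.1% | 265.5 |
| 10% | 66.7% | 98.8% | 304 |
| 12% | 71.1% | 98.6% | 342 |
| 15% | 76.1% | 98.2% | 399 |

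From 5% to 15%, PPV moves 27.5 points and NPV 1.2 points. The problem is essentially one of PPV.

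**Two separate sets of 2250 with an identical device.** The expected z is the PPV difference divided by √[PPV₁(1 − PPV₁)/n₁ + PPV₂(1 − PPV₂)/n₂], where n is the number of PCR positives.
- 8% versus 10%: 0.0565/0.0403 = 1.40. Chance of |z| > 1.96: about 29%.
- 8% versus 12%: 0.1004/0.0387 = 2.59 (two-sided p about 0.01). Chance: about 74%.

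**How the result depends on the central set chosen.** Take 8% in the first half and 12% in the second.
- Central set is the first half only: 61.0% against 71.1%, a gap of about 10 points.
- Central set is every sample with a central result: positivity averages 10%, giving 66.7% against 71.1%, a gap of 4.4 points.
- Central set is the later samples only, tested both ways: each sample has one paired culture whichever PCR run is scored. Positivity is identical, so the gap from this source is zero.

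**After standardisation.** Putting each set's own Se and Sp into the formulas at a common p = 10% returns PPV 66.7% and NPV 98.8% in both sets, so an identical device shows no difference.

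**The case against.** The strongest reply is that later samples are tested both ways, so a paired analysis is available in which the artefact vanishes. That is correct, and it is the basis of the fix. But section 5.1 does not call for pairing, and a set defined by having been tested centrally most naturally includes the central-only half.

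Second, no passage shows that positivity will differ. The contrast in site mix should not be overdrawn either. Reading Table 1 column by column, more than 15 sites are open from the column with 1103 cumulative samples, the previous column showing 864. So about 2250 − 864 = 1386 of the first 2250 samples (62%) accrue with the full network open. This stands: the effect is possible, not established.

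Third, section 5.1 plans confidence limits and no significance test on PPV. The 29% to 74% therefore describes what would happen if the difference were tested.

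Fourth, a reader might infer from section 11.2 that predictive values will be used to judge the device across types of patient. The text does not support that. The sentence on predictive values follows the whole-population 2×2 tables, the sub-analysis sentences name no metric, and sensitivity and specificity are given the main role. The choice may properly be made in a statistical analysis plan that is not shown.

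Fifth, a lower PPV where positivity is low is a true statement of what a positive result means there. It misleads only when taken as evidence about the device. That is why reporting predictive values is no error, while comparing them crudely between testing locations is.

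**Conclusion.** The concern holds for the POC-versus-central comparison in section 5.1. As written, crude PPV and NPV are compared between sets that may differ in culture positivity, unless the analysis is confined to samples tested both ways. An unchanged device with Se 90% and Sp 95% would then show PPVs anywhere from 48.6% to 76.1% over an assumed positivity range of 5% to 15%. NPV would barely move. The 29% to 74% chance of a nominally significant PPV difference rests on assumed positivities of 8% versus 10% up to 8% versus 12%, on separate sets of 2250, and on a test being done.

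One might go further and say that an identical device will appear to perform differently. The documents do not support that: it requires unequal positivity, and the protocol gives no rates by phase, site or type of patient. Sensitivity and specificity do not shift through positivity alone, and the whole-population primary estimates are unaffected. The zero artefact in samples tested both ways applies to the paired-culture reference; the resolved (fair umpire) reference was not worked here.

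**What to change.** In section 5.1, state that conclusions about POC versus central performance rest on sensitivity and specificity, compared in pairs within the later samples that have both results. Report PPV and NPV for each set descriptively, beside that set's culture positivity, or standardised to the overall study positivity with the formulas above. Standardised values add no information beyond sensitivity and specificity; their use is to put those on a familiar scale.

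Apply the same rule to any predictive values reported in the section 11.2 sub-analyses. Keep PPV and NPV for the whole population as they are.

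The cost is some wording and a few table rows, from data already collected. The paired comparison uses a smaller sample. With about 2250 samples and 10% positivity there are 225 culture positives, so sensitivity in one arm of the pair has a 95% half-width of 1.96 × √(0.9 × 0.1/225) = 3.9 points, against 2.8 points with all 450. Pairing removes differences in case mix between the two sets, which a comparison with the early samples cannot do.

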The concept of a 'golden hour' of assessment and intervention, initially described in other clinical settings, is therefore now well established in sepsis management¹². In SSC guidelines, both blood culturing and the administration of broad-spectrum empirical antibiotic treatment are recommended in the first hour after the recognition of potential sepsis. A 2010 review of the implementation of SSC guidelines across two continents demonstrated a 5.4% improvement in mortality even with only limited compliance¹⁶ although several studies also show that the empirical antibiotics received by 20-40% of patients in ICU are found to be inappropriate when the pathogen is later identified^{13,17}. Therefore, a rapid test for pathogen identification offers the opportunity to improve patients' treatment and outcomes.

Microbiological sampling in sepsis is independently associated with patients' survival¹⁸ and the SSC recommends at least two samples for traditional culture prior to the administration of antibiotics, within the first hour¹¹. Evidence on the sensitivity of blood cultures is conflicting¹⁹. The value certainly varies with the pathogen, but it is well accepted that it only approaches 100% by increasing the number of samples taken²⁰.

The emergence of multi drug resistant pathogens has gone from concerning case report to a challenging global priority over recent years- with particular relevance and incidence in intensive care settings worldwide^{21,22}. Empirical antibiotics contribute to resistance²³⁻²⁵ but remain essential to management with existing microbiological techniques that cannot provide a point of care result to identify a pathogen and guide more appropriate prescription²⁶. There is agreement that current diagnostic tools for sepsis are inadequate²⁷. The clinical need is clear: new, rapid, diagnostic methods that will facilitate prompt treatment with, effective, antibiotic therapy. To have an impact on patient management and outcomes, a novel diagnostic test in sepsis is required to be truly point of care, to provide ease of use, economy and portability, with a time to result of less than one hour.

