9. SCHEDULE OF ASSESSMENTS AND STUDY PROCEDURES

9.1 Schedule of Assessments

All patients will be evaluated during the study and data collected at each of the following time-points. For routinely collected clinical data the NHS record will be the source document and for study specific clinical measurements the CRF will be the source document.

Baseline

- Patient Demographics (date of birth, gender)
- Date and Time of ICU admission
- Suspected Source of Sepsis
- The Acute Physiology and Chronic Health Evaluation score (APACHE II) at ICU admission

At Sampling

- Site, Date and Time of sampling
- Previous Antibiotic regimens within 3 calendar days of sampling (Yes/No)
- Determinants of SOFA Score at time of sampling

Additional Assessments

- Paired blood culture result
- Multiplex PCR result
- Date and Time Multiplex PCR test completed
- Date and Time clinical team informed of blood culture result
- Results of additional blood and other sterile anatomic site cultures taken within +/-7 days of the research blood sample for suspected sepsis will also be recorded.
- Results of cultures from non-sterile anatomic sites within +/-3 days of the research blood sample for suspected sepsis will be recorded. Whether the treating physician judged this to represent a clinically-suspected focus of infection will also be recorded.

At Discharge

- Date of critical care discharge
- Date of hospital discharge

Mortality

- Date of death (within 28 days of recruitment)

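### Accuracy by prior antimicrobial exposure is judged against culture alone, so a lower PPV or specificity in exposed samples could reflect weaker culture, not weaker PCR

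*Protocol*

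**What the plan says.** Section 11.2 bases accuracy on sensitivity, specificity and "positive and negative predictive values calculated from comparison with conventional culture as the reference standard". It then announces sub-analyses by type of patient, which are to supply "assessments of the validity of POC testing by this method and device in the context of prior antimicrobial exposure", and likewise by diagnosis and patient condition. It names no other reference for them.

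Section 5.1 sets the primary measures as "calculated by using the paired blood culture as the reference standard". On the limits of that choice it says: "Acknowledging that there is no perfect reference standard for sepsis, a secondary analysis will be undertaken". Of this second reference, the fair umpire, it says: "This will be applied when the PCR test is positive and the paired blood culture is negative". A PCR-positive result is then confirmed by the same genus from blood or another sterile site within 7 days, or from a non-sterile site within 3 days if the clinical team judges that site a focus of infection. Section 5.1 asks for both references in the point-of-care versus central comparison. It does not mention the antimicrobial strata.

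Section 9.1 records antibiotic exposure in the 3 calendar days before sampling as yes or no. It also records blood and sterile-site cultures within 7 days either side of the sample, and non-sterile cultures within 3 days either side, without regard to the PCR result.

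**The concern.** A subgroup comparison of test accuracy is interpretable only if the reference works equally well in each subgroup. Prior antimicrobial exposure is a factor that may change the reference itself. If culture grows fewer organisms after antimicrobials while PCR still detects them, more true PCR detections fall in the PCR-positive, culture-negative cell and are scored as false positives. The difference between strata then mixes the behaviour of culture with that of PCR, yet section 11.2 presents it as the validity of the PCR test. The study could report that its test performs worse after antimicrobials when only the comparator has changed.

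**Working it through.** The protocol gives no accuracy figure for these strata, so there is none to reproduce. Its sample sizes reproduce to within one sample (385/0.10 = 3850 against 3851; 9/0.002 = 4500 against 4501) and are not affected.

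**Inputs**
- PCR sensitivity Se = 0.90 and specificity Sp = 0.95: section 11.1.
- True prevalence π = 0.125 in both strata: assumed. With culture sensitivity 0.80 it gives 10% culture positivity, in line with the 10% event rate in section 11.1.
- Culture sensitivity c = 0.80 unexposed, 0.40 exposed: assumed.
- Culture specificity 1, and test errors independent given true status: assumed.

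**Formulas against paired culture**
- PPV = πcSe / [πSe + (1−π)(1−Sp)]
- Specificity = 1 − [π(1−c)Se + (1−π)(1−Sp)] / (1−πc)

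The denominator of PPV does not contain c, so PPV is directly proportional to culture sensitivity.

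**Main illustration.** All PCR positives: 0.1125 + 0.04375 = 0.15625 in both strata.
- Unexposed: PPV = 0.0900/0.15625 = 57.6%; specificity = 1 − 0.06625/0.900 = 92.6%.
- Exposed: PPV = 0.0450/0.15625 = 28.8%; specificity = 1 − 0.11125/0.950 = 88.3%.
- Sensitivity is 90% in both.

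PCR is identical in the two strata. With 4501 samples split equally (assumed) and treated as independent, the 4.35-point specificity gap has standard error √(0.9264×0.0736/2026 + 0.8829×0.1171/2138) ≈ 0.0091. That is about 4.8 standard errors, giving power above 99% to declare the artefact significant.

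**Range.** Take PCR 90%/97%, prevalence 12% to 20% (equal in both strata), and culture sensitivity 70% to 80% unexposed and 40% to 60% exposed (all assumed except the 90%).
- Smallest gaps (π = 0.12, c = 0.7 v 0.6): specificity 93.6% v 92.5%, 1.1 points; PPV 56.2% v 48.2%, 8 points.
- Largest gaps (π = 0.20, c = 0.8 v 0.4): specificity 92.9% v 85.7%, 7.2 points; PPV 70.6% v 35.3%, 35 points.

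**Unequal prevalence**
- PCR 90%/95%, π = 0.125 v 0.06, c = 0.8 v 0.4: specificity 92.6% v 91.9%, nearly equal; PPV 57.6% v 21.4%.
- PCR 90%/97%, π = 0.15 v 0.08, c = 0.7 v 0.5: specificity 92.6% v 1 − 0.0636/0.960 = 93.4%. The gap reverses.

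**If PCR really is worse after antimicrobials.** In the main illustration, let exposed Se fall to 0.60. Exposed specificity is 1 − (0.045 + 0.04375)/0.95 = 90.7%, higher than the 88.3% found with an unimpaired test. Culture-based specificity therefore does not track PCR performance in either direction.

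**What the fair umpire recovers.** Let it confirm a share u of true PCR detections that culture missed (main illustration).
- u = 0.5 in both strata: PPV = 0.10125/0.15625 = 64.8% v 0.07875/0.15625 = 50.4%; specificity 93.8% v 91.5%.
- u = 0.5 unexposed, 0.25 exposed (the umpire is itself culture-based): PPV 64.8% v 39.6%; specificity 93.8% v 89.9%.
- u = 1: both gaps close (95% and 72% in each stratum).

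Because the umpire acts only on PCR positives, it also moves sensitivity apart: at u = 0.5, 0.10125/0.11125 = 91.0% v 0.07875/0.08375 = 94.0%.

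**The case against.** The strongest reply is that section 11.2 gives these sub-analyses a single sentence, and that section 11.5 leaves planned additional analyses to the statistical analysis plan. The choice of references to tabulate per subgroup is often made there. Section 5.1 already concedes that the reference is imperfect and supplies an umpire for the very cell at issue, and nothing forbids its use in the strata. Part of this stands: silence about the umpire alone would not be a finding. But section 11.2 is not silent. It fixes the comparator and names what the strata are to show, while section 5.1 spells out both references for a different comparison. A plan that follows this wording inherits the problem.

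Three stronger readings are tempting and are not supported:
- **That exposed samples are bound to show lower specificity.** This needs similar true prevalence in both strata, which no section states; the reversal shown in the working is possible.
- **That the protocol itself establishes that antimicrobials suppress culture but not PCR.** It does not. Section 3.2.1 says only that the sepsis guideline "recommends at least two samples for traditional culture prior to the administration of antibiotics", and that evidence on culture sensitivity is conflicting.
- **That the investigators intend to report a lower value as poorer PCR.** The text announces an assessment of validity and gives no such rule.

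**Conclusion.** The concern holds in conditional form. If prior antimicrobials reduce culture growth more than PCR detection, the planned strata cannot separate a weaker reference from a weaker test. PPV carries most of the effect: 8 to 35 points over the assumed range, and a halving in the main illustration. Specificity moves by 1.1 to 7.2 points when prevalence is equal in the strata, and may not move, or may move the other way, when it is not. Sensitivity is unaffected in this model. The sizes rest on assumed culture sensitivities and prevalences, perfect culture specificity and independent errors; the direction for PPV rests only on lower culture sensitivity with PCR and prevalence unchanged. A reader might infer that the overall primary analysis or the sample size is undermined. This point does not show that: it concerns the interpretation of one set of sub-analyses.

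**What to change.** In section 11.2, for the antimicrobial-exposure strata:

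1. Report specificity and PPV under both section 5.1 references, paired blood culture and fair umpire, keeping the umpire's definition including its non-sterile-site criterion.
2. Add a supporting analysis that applies the blood and sterile-site cultures already recorded within 7 days either side to all samples, whatever the PCR result, so that reclassification does not depend on the test under study.
3. Show culture positivity in each stratum.
4. State that a between-stratum difference in culture-based specificity or PPV describes agreement with culture and is not by itself evidence of lower PCR validity.

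The cost is this wording and one extra table from data already collected. Both references remain culture-based, so the artefact is reduced and not removed; item 4 is needed for that reason. The supporting analysis has its own weakness: an infection arising days after the sample would count as a PCR miss, so it should stand beside the two section 5.1 references and not replace them.
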